Study Duration	-Approximately four years; Because D2d is an event-driven trial, study duration is approximate only.
 Visits	-Thirteen scheduled visits: Screening, Baseline (BAS), Randomization (RAD), M03, M06, M12, M18, M24, M30, M36, M42, M48 and end-of-study. Additional visits may be required for confirmatory glycemic testing or safety evaluation, including scheduled visits beyond M48.
 Phone calls	-Eight scheduled telephone calls in between visits: M09, M15, M21, M27, M33, M39, M45. Additional calls may be required beyond M48.
Primary Outcome	Time to development of diabetes
Secondary Outcomes	
-Variability of response to vitamin D supplementation by several baseline characteristics: (1) race and ethnicity (as proxies for skin pigmentation); (2) BMI; (3) waist circumference; (4) age; (5) geographic location (proxy for sun exposure); (6) calcium intake (based on Food Frequency Questionnaire); (7) 25OHD concentration.
 
-Variability of response to vitamin D supplementation by adherence based on pills counts and by achieved 25OHD concentration.
 
-HbA1c, FPG and 2hPG as continuous variables.
 
-Insulin resistance and beta cell secretion (indices derived from the OGTT).
 
-Plasma 25OHD concentration and identification of phenotypic, including seasonal and geographic, characteristics associated with variability on achieved plasma 25OHD concentration.
 
-Blood pressure.
 
-Safety and tolerability of vitamin D supplementation.

Sample Size (total)	-2,382 participants randomized to vitamin D or placebo
 Participants per site	-Variable, depending on site's experience (~100 to 150 per site)
 Attrition rate	-15% (maximum) of the original cohort over the study period
Analysis Strategy	Kaplan-Meier estimates of "time to confirmed diabetes" distributions will be calculated for each treatment group. The log-rank test will then be used to perform an adjusted comparison of the time-to-event distributions in the two treatment groups. Cox proportional hazard models will be used to calculate an estimate of the adjusted hazard ratio. Pre-specified subgroup analyses will be performed in participant subgroups defined by baseline variables, and other variables, to gain information on predictors of response to therapy.

Schedule of Procedures

Point of Contact	Screening ¹	Baseline	Randomization	M03	M06	M09 (Phone)	M12	Interim Phone	Semi-annual	Annual	Confirm	As needed

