4. Symptom-directed physical examination will be done as needed (e.g. if adverse events are reported at a follow-up visit).
5. Vital signs include height, weight, blood pressure and heart rate.
6. Food frequency questionnaire (FFQ) will be completed at baseline, and at visits M12 and M36 only in participants free of diabetes.
7. Lifestyle counseling includes written educational materials at baseline. During the trial, participants will join the D2d Support and Education Program.
8. Laboratory and urine testing is done after 8 hours of overnight fasting.

9. Pregnancy test is required for women of reproductive potential at screening. Point-of-care urine testing will be done followed by confirmatory blood testing, if point-of-care test is positive. If point-of-care urine testing is not an option, a urine or serum test will be done at the site's laboratory. Pregnancy testing is done during the study if the participant reports missing two consecutive menstrual periods, based on the woman's typical menstrual cycle. During pregnancy, participant becomes "inactive" and resumes participation after delivery.
10. HbA1c, FPG, 2hPG and urine calcium-creatinine ratio are measured by the Central Laboratory in real time (see text for details on reporting of results). Other outcome laboratory tests (e.g. 25OHD, insulin) are done at a later time
11. At screening, HbA1c and FPG may be done by the site's local laboratory or any other laboratory (including the LCBR at U. Vermont, which serves as the study's Central Laboratory).
12. 2hPG, Glu₃₀, and insulin (Ins₀, Ins₃₀, Ins₁₂₀) are performed at baseline, and at annual visits in participants free of diabetes.
13. Semi-annual confirmatory testing: If FPG \geq 126 or HbA1c \geq 6.5% at the semi-annual visit, a confirmatory visit is conducted and only the abnormal test is repeated.
14. Annual confirmatory testing: If FPG \geq 126 or HbA1c \geq 6.5% or 2hPG \geq 200 mg/dL at the annual visit, a confirmatory visit is conducted that may include an OGTT (see text for details).
15. Letter informing participant's physician(s) of her patient's participation in D2d.
16. Letter informing participant's physician(s) of her patient's continued participation in D2d, and the outcome of glycemic testing or diabetes diagnosis according to the study's criteria.

The last scheduled visit (semi-annual or annual) serves as the end-of-study visit. Procedures done will depend upon the scheduled visit with which it coincides (see text).

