6.5 Screening & Assessment of Eligibility

The goals of the formal screening visit are to: (1) complete the informed consent process and obtain written informed consent; (2) assess eligibility. Volunteers will be seen at each site in the morning after an overnight fast for a screening visit lasting approximately 1.5 hours. At this visit, after written informed consent is obtained (unless it has been obtained already during a pre-screening optional visit), the following will be performed: medical history, vital signs (height, weight, blood pressure and heart rate), and laboratory measurements to assess eligibility for the study (complete blood count, liver function tests [AST, ALT], serum calcium, serum creatinine and estimation of creatinine clearance, pregnancy test for women with reproductive potential, FPG and HbA1c). Laboratory measurements will be performed locally, (i.e., by the site's clinical laboratory) or by any other laboratory (e.g., LCBR at U. Vermont, which serves as the study's Central Laboratory), depending on site's preference. All screening laboratory results will be reported to volunteers and their health care provider(s).

Volunteers will be invited to the baseline visit if they meet the following criteria at the screening visit: (see Figure 6.1):

[figure not shown]
- a) FPG and HbA1c results are within range, as defined by site-specific criteria. At the screening visit, sites use a specific algorithm to determine whether the FPG and HbA1c values fall within range to proceed to the baseline visit. A default algorithm has been developed for all sites to use initially (shown at the bottom of Figure 6.1). As needed, the success of the default algorithm for that site is reviewed and, if appropriate, a site-specific algorithm can be developed to maximize the screened-to-randomized ratio.
- b) All other non-glycemic inclusion criteria and meet none of the exclusion criteria

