
8. PROCEDURES AND OUTCOME MEASURES

8.1 Study Visits and Phone Calls

The baseline visit (BAS) should occur after the results of screening lab analyses have been reviewed and preliminary eligibility determined, within 6 weeks of the screening visit. The site investigator will review the results of the baseline visit laboratory measures and determine if the participant meets the study eligibility criteria. If eligibility is confirmed, the participant will return for the randomization visit, within 3 weeks of the baseline visit.

Follow-up visits will occur at 3 months (M03), 6 months (M06), and every 6 months thereafter (e.g. M12, M18) until study end. Follow-up visits should occur within ± 2 weeks of the scheduled date. However, follow-up visits may be postponed for up to 8 weeks if a temporary concomitant condition exists that would affect glucose tolerance (e.g. infection) or its assessment (e.g. blood transfusion or blood donation) or for any other administrative or social reason. The reason for the postponement of the visit will be documented in the electronic data capture system.

The last scheduled visit (semi-annual or annual) will serve as the end-of-study visit. When D2d is approximately within 2 months of reaching its goal of the number of diabetes events needed, a study-wide announcement will notify sites that all subsequent scheduled visits will be considered the end-of-study visit. At the end-of-study visit, activities will include those that would occur at the scheduled semi-annual (e.g., fasting labs) or annual visit (e.g., OGTT).

During each follow-up visit, the research coordinator will assess study pill adherence, and question the participant regarding the occurrence of adverse events or changes to medical history and concomitant medication use.

Phone contact is scheduled at the midpoint of each 6-month follow-up visit after the 6-month visit (e.g. M09, M15). Participants will be contacted by the research coordinator to encourage adherence, assess for adverse events or changes to medical history and concomitant medication use, and be reminded of their upcoming visit. Participants may be contacted at other times between visits for invitations to Support and Education Program events, to respond to questions, or other study-related issues. These contacts may be conducted via email, text, or other means of communication, based on participants' preference.

Unscheduled visits may occur between scheduled visits for the following reasons:

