8.3 Vital Signs

Vital signs composed of height, weight, blood pressure and heart rate will be assessed at screening, baseline and all follow-up and unscheduled visits. Waist circumference will be measured at baseline only. Results of these measurements will be reported to participants, as it is not feasible to keep these data masked from participants.

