3.2.2 Secondary outcomes – independent of the primary outcome: continuous variables

- Blood pressure (baseline and semi-annually)
- Cardiovascular risk factors: cholesterol profile, C-reactive protein, urine albumin excretion (baseline, M12 and M24)
- Atherosclerotic Cardiovascular Disease (ASCVD) ACC/AHA composite risk score (baseline, M12, M24)

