5 SECONDARY ANALYSES

Effect of vitamin D supplementation on secondary outcomes (**as continuous variables**) will be based on a linear mixed model and account for within subject correlation in repeated measurements over time. The overall mean difference between vitamin D and placebo groups for these analyses will be tested using the nominal 0.05 type 1 error rate *without adjustment for multiple comparisons*.^{11,12}

Some of these analyses (e.g., insulin secretion, cardiovascular risk factors) will not be presented in the main manuscript but in separate publications.

5.1 Related to the primary outcome (i.e., diabetes).

Change from baseline in:

- HbA1c, FPG and 2hPG
- Insulin secretion, sensitivity and disposition index. (indices derived from the OGTT).

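### The SAP does not provide for using the screening blood pressure as a second pre-randomisation reading, and so gives up some precision on a secondary outcome

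*Protocol*

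**What the plan says.** Blood pressure is a named secondary outcome (Protocol Synopsis, 3.2.2 and 9.2). Protocol 8.3 sets the measurement schedule: "Vital signs composed of height, weight, blood pressure and heart rate will be assessed at screening, baseline and all follow-up and unscheduled visits". Protocol 6.5 confirms that the screening visit includes "medical history, vital signs (height, weight, blood pressure and heart rate), and laboratory measurements to assess eligibility for the study". The Schedule of Procedures marks vital signs at screening and at baseline, and none at the randomisation visit; its note 5 reads "Vital signs include height, weight, blood pressure and heart rate". Participants with separate screening and baseline visits therefore have two pre-randomisation readings. Protocol 6.5 also allows a combined screening/baseline visit, which gives only one.

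SAP 3.2.2 gives the time points as "Blood pressure (baseline and semi-annually". SAP 5.2 lists blood pressure under change from baseline, with a test of interaction by race. Under SAP 5, the analysis of continuous secondary outcomes "will be based on a linear mixed model and account for within subject correlation in repeated measurements over time", and the overall mean difference between arms "will be tested using the nominal 0.05 type 1 error rate". The SAP does not mention the screening reading, does not define baseline blood pressure as an average, and does not state adjustment for baseline.

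**The concern.** A blood pressure taken at one visit is a noisy measure of a person's usual pressure. In a change score the error in the single baseline reading enters every follow-up difference for that person, and extra follow-up visits do not average it out. A second reading, unaffected by treatment, is already scheduled. Leaving it out widens the interval for the blood pressure effect and for its race interaction beyond what the collected data require. What is at stake is precision on a secondary outcome, not validity.

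**Working it through.** **Inputs from the documents.** 2,382 participants randomised 1:1, so 1,191 per arm. Mean follow-up is about 3 years (Protocol 4.3.5), so about six semi-annual readings, M06 to M36. The documents state no SD, correlation or power for blood pressure, so there is no plan figure to reproduce.

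**Assumed.** The between-visit correlation, and an SD of 15 mmHg where a result is given in mmHg. Screening is placed 1.5 months and baseline 0.5 months before randomisation, inside the schedule's windows.

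**Formulas**, in units of the single-reading variance. Vf is the variance of the mean of the follow-up readings, Vb the variance of the baseline measure, and c the covariance of the two.
- Raw change: V = Vf + Vb − 2c
- Baseline as covariate: V = Vf − c²/Vb

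**Constant correlation ρ**, r follow-up readings, p pre-randomisation readings.
- Raw change reduces to (1 − ρ)(1/r + 1/p). With r = 6 the bracket falls from 1/6 + 1 = 1.167 to 1/6 + 1/2 = 0.667, a cut of 43% at any ρ. With r = 4 it falls from 1.25 to 0.75, a cut of 40%.
- Covariate: V = (1 + (r − 1)ρ)/r − pρ²/(1 + (p − 1)ρ). At ρ = 0.6 and r = 6, V falls from 0.667 − 0.360 = 0.307 to 0.667 − 0.450 = 0.217, a cut of 29%. For ρ from 0.4 to 0.8 the cut is 20–37%. At ρ = 0.4 and r = 4 it is 18%.

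**Decaying correlation**, r = 6, with correlation at a gap of d months equal to a + b·φ^(d/6).

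| a, b, φ | Screening–baseline corr. | Baseline–M36 corr. | Covariate V, one → two readings | Raw change V, one → two readings |
|---|---|---|---|---|
| 0.4, 0.2, 0.5 | 0.58 | 0.40 | 0.359 → 0.311 (−13%) | 0.683 → 0.475 (−30%) |
| 0.3, 0.3, 0.5 | 0.57 | 0.30 | 0.364 → 0.333 (−8%) | 0.791 → 0.580 (−27%) |
| 0.5, 0.2, 0.7 | 0.69 | 0.52 | 0.342 → 0.285 (−17%) | 0.529 → 0.378 (−29%) |
| 0, 0.7, 0.8 | 0.67 | 0.18 | 0.412 → 0.395 (−4%) | 0.850 → 0.700 (−18%) |

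First row in full: Vf = 0.5448. With one reading Vb = 1 and c = 0.4310; with two, Vb = 0.7891 and c = 0.4293.
- Raw change: 0.5448 + 1 − 0.8620 = 0.683, then 0.5448 + 0.7891 − 0.8586 = 0.475.
- Covariate: 0.5448 − 0.4310² = 0.359, then 0.5448 − 0.4293²/0.7891 = 0.311.

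Over a wider set of such patterns the cuts run to about 4–18% (covariate) and 16–31% (raw change). These are not bounds. Steeper decay gives less, and a flatter correlation moves towards the constant-correlation figures.

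**In mmHg, first row.** The difference detectable with 80% power is 2.80 × 15 × √(2V/1191).
- Raw change: 1.42 with one reading, 1.19 with two.
- Covariate: 1.03 with one reading, 0.96 with two.

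Entering baseline as a covariate (1.42 to 1.03) gains more here than averaging alone (1.42 to 1.19). The fix therefore asks for both.

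**Combined visits.** If a share q of participants had one combined visit, the raw-change cut is multiplied by (1 − q). With q assumed at 25%, the 30% in the first row becomes about 23%. The documents do not give q.

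**The case against.** **The gain is small and rests on assumptions.** This stands. The larger percentages need either constant correlation over years or a raw change score. With covariate adjustment and decay, the example moves the detectable difference by 0.07 mmHg (1.03 to 0.96). No power target for blood pressure is missed.

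**Screening pressure is also an eligibility measure.** Exclusion criterion 25 uses blood pressure, and re-screening after treated hypertension is allowed, so the reading is selected and subject to regression to the mean. Both effects precede randomisation and act alike in the two arms. Using the qualifying screening visit deals with re-screening.

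**A reader might infer that the SAP has decided to discard these readings.** The documents do not support that. The SAP lists time points and excludes nothing expressly, so it is under-specified.

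**A reader might also infer that the M03 reading is wrongly left out and should be pooled.** M03 is a follow-up visit: "Follow-up visits will occur at 3 months (M03), 6 months (M06), and every 6 months thereafter". But the protocol expects 25OHD to reach steady state within 4 months (4.3.5), and M03 falls at day 77 to 105, so the effect there may be partial. With six semi-annual visits and constant correlation, pooling M03 cuts variance by only about 2–4%. If the M03 effect is a fraction f of the full effect, the pooled mean effect is (6 + f)/7 of full. At f = 0.8 that is 0.971, and at ρ = 0.6 the net efficiency is 0.96 (raw change) or 0.97 (covariate), which is a loss. Break-even is near f = 0.9. With decaying correlation M03 saves about 7–9% and break-even is lower, roughly 0.55–0.75. Leaving M03 out of the averaged effect is therefore a defensible choice.

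**Conclusion.** The point holds as a minor, optional improvement in precision. A second unbiased pre-randomisation reading is scheduled, and the SAP makes no provision for it. Its use would cut the variance of the blood pressure comparison by about 4–18% with baseline as a covariate, or about 16–31% for raw change, under assumed decaying correlations. Under constant correlation the figure is about 18–43%. The cut is smaller in proportion to the share of combined visits. The race interaction would gain similarly if the correlation is alike across race groups. The direction does not depend on the assumed values; the size does. Nothing here biases the blood pressure comparison, and the primary diabetes analysis is untouched.

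**What to change.** Before unmasking, amend SAP 3.2.2 and 5.2 as follows:
- Define baseline blood pressure as the mean of the qualifying screening-visit reading and the baseline-visit reading, or the baseline reading alone where the two visits were combined.
- State that this baseline enters the linear mixed model as a covariate.
- Do not pool M03 into the overall mean effect. If M03 is used, enter it only as a separate visit term.

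The cost is a sentence or two in the SAP. The readings are already scheduled, so no new measurement is needed, and fixing the definition in advance removes a later analyst choice.

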2. BACKGROUND, RATIONALE AND SIGNIFICANCE

2.1 Background and Rationale

The incidence of diabetes is increasing at an alarming rate both nationally and worldwide with 1.9 million new cases diagnosed in 2010 in the US alone,¹ with nearly 9 out of 10 new cases due to type 2 diabetes. The diabetes population and related costs are expected to more than double in the next quarter century,² as more than 79 million Americans are at risk of developing diabetes.^{1,3,4} In clinical trials, lifestyle changes aiming at weight loss are successful at reducing risk of diabetes.⁵⁻⁹ However, long-term weight-maintenance in the clinical setting has proved elusive. Moreover, even after successful weight loss, substantial residual risk (~40-50%) remains and may be attributable to modifiable factors.¹⁰ Several medications that are used to treat established diabetes have also been studied for prevention of diabetes and many have been shown to delay incident diabetes;^{9,11-17} however, the role of pharmacologic agents for prevention of diabetes is not clear.⁹ Therefore, identification of easily modifiable risk factors that are safe, inexpensive and acceptable is urgently needed to prevent type 2 diabetes and decrease disease burden.

Based on recent evidence,¹⁸⁻⁴⁴ which has been synthesized in systematic reviews,⁴⁵⁻⁴⁸ suboptimal vitamin D status has emerged as a potential contributor to the pathophysiology of type 2 diabetes. However, the evidence to support general supplementation for prevention of type 2 diabetes does not currently exist because the favorable association between vitamin D status and type 2 diabetes risk is based almost exclusively on observational studies, which may be confounded by a variety of factors and there are no published trials specifically designed and powered to test the effects of vitamin D supplementation on the development of type 2 diabetes. The D2d study will test this hypothesis by examining the causal relationship between vitamin D and development of diabetes in persons at risk for diabetes. If the hypothesis of a link between vitamin D and type 2 diabetes is confirmed by the proposed trial, the results will have significant public health implications since vitamin D status has declined in the US over the last decade⁴⁹ and vitamin D supplementation can be implemented easily and inexpensively in clinical practice.

2.2 Biologic plausibility of an association between vitamin D and type 2 diabetes

When glucose intolerance and type 2 diabetes develop, impaired pancreatic beta-cell function, insulin resistance and systemic inflammation are often present.^{50,51} There is evidence that vitamin D influences these mechanisms, as described next.

Vitamin D and pancreatic beta-cell function / insulin secretion

In *in vitro* and *in vivo* studies, vitamin D deficiency impairs glucose-mediated insulin secretion from beta-cells,⁵²⁻⁵⁵ while vitamin D supplementation restores insulin secretion.^{52,54-57} Vitamin D may have a direct effect on beta-cell function mediated by binding of the circulating active form, 1,25(OH)₂D, to the vitamin D receptor, which is expressed in pancreatic beta-cells.^{58,59} Furthermore, mice lacking a functional vitamin D receptor show impaired insulin secretory response following a glucose load, attributed to a decrease in insulin synthesis resulting in a reduction in the amount of insulin stored in the beta cell.⁵⁸ The presence of the vitamin D response element in the human insulin gene promoter⁶⁰ and transcriptional activation of the human insulin gene by 1,25(OH)₂D⁶¹ further support a direct effect of vitamin D on insulin synthesis and secretion. Alternatively, activation of vitamin D also occurs within the pancreatic beta cell by the 25-hydroxyvitamin D-1 α -hydroxylase enzyme (CYP27B1), which is expressed in pancreatic beta cells.⁶² Such a mechanism allows for a paracrine effect of circulating 25OHD. An indirect effect of vitamin D on the beta cell may be mediated via its regulation of extracellular calcium concentration and calcium flux through the beta cell.⁶³ Insulin secretion is a calcium dependent process,⁶⁴ therefore, alterations in calcium flux can have an effect on insulin

secretion.⁶⁵⁻⁶⁷ Vitamin D also regulates calbindin, a cytosolic calcium-binding protein found in many tissues including beta cells.^{59,68} Calbindin is a modulator of depolarization-stimulated insulin release via regulation of intracellular calcium.⁶⁹ Finally, vitamin D may promote beta-cell survival by modulating the generation (e.g. through inactivation of nuclear factor-kB [NF-kB]) and effects of cytokines.^{70,71} In some but not all cross-sectional human studies, an association between the blood 25OHD concentration and insulin secretion has been reported.^{72,73,74}

Vitamin D and insulin sensitivity

In peripheral insulin-target cells, vitamin D may enhance insulin sensitivity in several ways. Vitamin D may directly augment insulin sensitivity by stimulating the expression of insulin receptors,^{60,61,75,76} The active form, 1,25(OH)₂D, enters insulin-responsive cells and interacts with the vitamin D receptor, activates the vitamin D receptor-retinoic acid X-receptor (RXR) complex which, in turn, binds to a vitamin D response element found in the human insulin receptor gene promoter. The result is enhanced transcriptional activation of the insulin receptor gene, which increases the total insulin receptor number without altering receptor affinity. Vitamin D may also enhance insulin sensitivity by activating peroxisome proliferator-activated receptor delta (PPAR-δ), a transcription factor implicated in the regulation of fatty acid metabolism in skeletal muscle and adipose tissue.⁷⁷ An indirect effect of 1,25(OH)₂D on insulin sensitivity might also be exerted via its important and well-recognized role in regulating extracellular calcium concentration and flux through cell membranes. Calcium is known to be essential for insulin-mediated intracellular processes in insulin-responsive tissues such as skeletal muscle and adipose tissue,^{78,79} with a very narrow range of intracellular calcium needed for optimal insulin-mediated functions.⁸⁰ Changes in intracellular calcium in insulin target tissues may contribute to peripheral insulin resistance⁸⁰⁻⁸⁷ via impaired insulin signal transduction^{87,88} leading to decreased glucose transporter activity.⁸⁷⁻⁸⁹ Hypovitaminosis D also leads to increased parathyroid hormone concentration, which has been associated with increased insulin resistance.^{90,91} Vitamin D may also affect insulin resistance indirectly through the renin-angiotensin-aldosterone system.⁹²⁻⁹⁵ Finally, vitamin D insufficiency is associated with increased fat infiltration in skeletal muscle, independent of body mass, which is thought to contribute to decreased insulin action.⁹⁶ In observational human studies, low vitamin D status (assessed by self-reported vitamin D intake or blood 25OHD concentration) has been associated with simple indices of insulin resistance, including measurements of fasting insulin and homeostasis model assessment (HOMA-IR),^{20,29,35,72,73,97-101} but the association is not consistent.^{74,99,102}

Vitamin D and systemic inflammation

Systemic inflammation, via an increase in pro-inflammatory cytokines, plays an important role in the pathogenesis of type 2 diabetes, mostly by promoting insulin resistance; however, pancreatic beta cell function may also be affected via cytokine-induced apoptosis.^{50,103-105} Vitamin D can lessen the effects of systemic inflammation on type 2 diabetes risk in several ways. For example, 1,25(OH)₂D may improve insulin sensitivity and protect against beta cell cytokine-induced apoptosis by directly modulating the expression and activity of cytokines.^{71,106-108} One such pathway may be through down-regulation of NF-kB, which is a major transcription factor for TNF-α and other inflammatory mediators.¹⁰⁹ Another pathway that may, at least in part, mediate the anti-apoptotic effect of 1,25(OH)₂D on beta cell is through counteracting cytokine-induced Fas expression.¹¹⁰ Several other immune-modulating effects of 1,25(OH)₂D (e.g. blockade of dendritic cell differentiation, inhibition of lymphocyte proliferation, inhibition of foam cell formation and cholesterol uptake in macrophages, enhanced regulatory T-lymphocyte development)^{107,111} may provide additional pathways of protection against inflammation-induced type 2 diabetes risk. In observational human studies, low vitamin D status (assessed by self-reported vitamin D intake or blood 25OHD concentration) has been associated with elevated concentration of markers of systemic inflammation in some^{101,112,113} but not all studies.^{20,114-116}

2.3 Evidence from human studies for a link between vitamin D and type 2 diabetes

Observational Studies

The strong data in humans that link vitamin D to type 2 diabetes are primarily from observational studies. Cross-sectional studies have generally reported inverse associations between vitamin D status and prevalent hyperglycemia.^{35,38,40,41,45,73,97,99,117-131} In a large cross-sectional study with data from the U.S. based National Health Nutrition Examination Survey (NHANES), serum 25OHD concentration was inversely associated with prevalence of diabetes in a dose-dependent pattern in non-Hispanic whites and Mexican-Americans, after multivariate adjustment, including BMI.⁹⁷ In this study, there was no association in non-Hispanic blacks despite lower 25OHD concentration found in this racial group, which may be explained by the observation that non-whites exhibit a different vitamin D, calcium and PTH homeostasis compared to whites.¹³² However, a subsequent analysis from NHANES did not find an interaction between blood 25OHD concentration and race or ethnicity on glycemic outcomes.³⁵ More recent studies using NHANES data have repeatedly confirmed the inverse association between 25OHD and glycemia,^{35,121,133-135} which has also been reported in other large cohorts from the U.S.⁹¹, Europe¹³⁶ and China.¹⁰⁰ Cross-sectional studies, however, are difficult to interpret, as the directionality of the association (cause and effect) cannot be determined.

To overcome the inability of cross-sectional studies to establish the direction of the causality between vitamin D status and type 2 diabetes related parameters, longitudinal observational studies have been conducted where vitamin D status is assessed prior to the development of the outcome of interest, incident type 2 diabetes. There are 14 studies (from 15 cohorts) that have reported on the longitudinal association between vitamin D status (intake or 25OHD) and risk of type 2 diabetes.^{18,21,22,25,26,28,36,37,39,42-44,137} Nearly all of them have reported an inverse association between vitamin D status (intake or 25OHD concentration) and incident type 2 diabetes. A recent meta-analysis, examining only 25OHD concentration as the predictor,¹³⁸ identified 9 publications that provided data from 13 cohorts involving 65,721 participants and 3,567 incident cases of diabetes.^{22,25,28,37,39,42-44,137} Comparing the highest to the lowest category of 25OHD, the pooled relative risk for incident diabetes was 0.65 (95% CI, 0.55-0.77). A linear trend meta-regression analysis showed that each 4 ng/mL increment in 25OHD was related to a 4% lower risk.

Intervention Studies

Several trials have reported the effect of vitamin D supplementation on glycemia^{19,34,139-147} or incident diabetes by self-report. In nine trials that included participants with *normal glucose tolerance*, supplementation with vitamin D had overall a neutral effect on glycemic measures or incident diabetes.^{19,34,139,141,142,144,145,148,149} However, several of these trials were designed for non-glycemic outcomes and the analyses on diabetes were *post-hoc* and *all trials* (except for the Women's Health Initiative trial, WHI) were *underpowered for glycemic outcomes*. In several trials, adherence with supplementation was suboptimal. For example, in a post-hoc analysis of the RECORD trial (a community-based trial designed for bone outcomes),¹⁴⁸ 800 IU/day of vitamin D₃ did not change risk of *self-reported type 2 diabetes*; however, among study participants who were highly compliant with supplementation, there was a notable trend towards reduction in type 2 diabetes risk with vitamin D₃ (odds ratio 0.68; 95%CI 0.40, 1.16), which *highlights the importance of efficacy vs. effectiveness trials*. Importantly, several trials supplemented with infrequent (weekly or monthly) large doses of vitamin D, a commonly used clinical approach, which may not be a desirable physiologic method for supplementation and may be counterproductive.¹⁵⁰

The potential effect of vitamin D appears to be more prominent among persons with pre-diabetes. In a post-hoc subgroup analysis conducted using data from a completed trial designed for fractures, combined vitamin D₃ (700 IU/day) and calcium carbonate (500 mg/day) supplementation improved fasting plasma glucose (FPG) and insulin resistance (HOMA-IR) among adults with glucose

intolerance at baseline,¹⁹ suggesting that *vitamin D may benefit only individuals at high risk (e.g. pre-diabetes)*. In this study, *the reduction in FPG over 3-years was similar to the reduction in FPG achieved with metformin or lifestyle, in the Diabetes Prevention Program, which was associated with a 31-58% decrease in incident diabetes.*⁵ In the Calcium and Vitamin D for type 2 Diabetes Mellitus (CaDDM) study, a 2x2 factorial design trial, vitamin D supplementation improved - disposition index, a composite measure of beta cell function that accounts for the prevailing insulin sensitivity, in participants with pre-diabetes but without regard to baseline vitamin D status or calcium supplementation.²⁴ In another intervention study, very similar to the CaDDM trial, where vitamin D was given without a placebo, insulin sensitivity improved after 4 weeks of vitamin D administration in persons with pre-diabetes.¹⁵¹ *On the basis of these observations, in the proposed D2D trial, a pre-diabetes population is targeted.*

